1. FINAL PROTOCOL

Overview

This study will enroll 150 older spousally-bereaved adults who are high risk for major depressive disorder (MDD) due to subthreshold symptoms of depression. These subjects will be randomly assigned to digital monitoring of sleep, meals, and physical activity behaviors or enhanced usual care. Subjects will be followed for 12 months after the intervention. We selected a 12-week intervention because this length of time was (a) sufficient to observe change in the proposed mechanism of action (circadian rest activity rhythm); and (b) acceptable to participants in our pilot RCT.

Participants and Study Design

Participants. A total of 150 older adults will be enrolled in the proposed study. We have chosen to target spousally-bereaved adults aged 60 years and older for the following clinical and methodological reasons: (a) adults aged 60 years and older experience bereavement differently than younger age groups because older adults are also experiencing declines in physical, mental, and cognitive health that may inhibit adaptive functioning following bereavement; (b) recently bereaved elders (≤ 12 months post spousal death) are at heightened risk for depression and other mental health problems related to poor self-care; (c) there is an urgency to understand strategies to modify the trajectories of depressive symptoms in bereaved elders already at risk for developing depression (indicated prevention) given the growing population of older adults who become bereaved each year, (d) examining bereaved elders who are at risk for depression is necessary to observe changes in response to the intervention over the short period of time that is

feasible to conduct a RCT. Targeting older adults who are not at risk for depression would increase the likelihood of ceiling effects.

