2. FIDELITY MONITORING PLAN

Fidelity to digital monitoring was calculated by summing the number of times participants completed the digital diaries: 2 diaries per day for 3 months = 168 possible diaries. Using the gold-standard for coding fidelity of motivational interviewing – the Motivational Interviewing (MI) Treatment Integrity Coding Manual – four components of MI will be coded during each health coaching session: open-ended questions, affirmations, reflective listening, and summarizing statements.¹¹ All MI sessions were audio recorded and 20% of sessions (from early, middle, and late intervention) were randomly selected for fidelity ratings (by a MI expert) to ensure maintenance of treatment specificity and integrity. The MI expert suggested therapeutic

strategies over the course of contact with participants to ensure fidelity to the desired target – regularity of sleep, meals, and physical activity.

Table 1 shows our fidelity plan for monitoring intervention delivery, receipt, and enactment.¹²

Using the gold-standard for coding fidelity of motivational interviewing – the Motivational

Table 1. Fidelity Monitoring Plan	
Domain	Monitoring procedures
Delivery Is the intervention delivered as intended?	
 - Monitoring checklists for each session (BL, T2, T3, T4, T5) which provide quantification of adherence to session protocols 
Interventionists (for MI)
 
 - Use of a treatment manual - Certified in the use of MI for behavior change by the Motivational Interviewing Network of Trainers (MINT) - Completion of session-by-session tracking forms - Audiotaped sessions
Receipt Did participants receive intervention as intended?	
 - Tracking the # of diaries participants enter in the tablet - Tracking the # of times performance feedback was viewed - Checking in during MI sessions to evaluate what works and what is not working - Identification of any participant barriers to participation (e.g., use of a paper diary in lieu of the tablet because of dexterity barriers)
Enactment Did participants enact the behavioral skills imparted?	
 - Attainment of personal health goal(s) - Follow-up survey of awareness of daily routine - Follow-up survey of continued self-monitoring and progress towards health goal

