3. STATISTICAL DESIGN AND POWER

Descriptive Statistics

Data will be examined descriptively using observed means, standard deviations, and percentiles for continuous variables; and frequencies and proportions for categorical variables. We will

examine continuous variables to determine if distributional assumptions, for e.g., normality and homoscedasticity, are satisfied. Transformations or nonparametric techniques will be applied as needed. Statistical comparisons will be performed to compare the intervention and control arms with respect to demographic characteristics and important health characteristics at baseline. Standard techniques include t-tests for continuous variables and Fisher's exact test and/or Pearson χ^2 procedures for categorical variables. The baseline values of the outcome variables will be analyzed in a similar manner to determine whether any systematic differences between the treatment arms remained after randomization. The proposed study is a randomized clinical trial with repeated measures, with the purpose of (1) assessing change over time for the intervention group relative to the enhanced usual care group and (2) comparing the change between the intervention and enhanced usual care group with regards to the primary outcome (depression symptoms).

Randomization

Groups will be randomized using a 1:1 randomization scheme to minimize threats to internal validity.¹⁴ We will use permuted-block randomization where subjects are allocated randomly within blocks known only to statisticians. Given the possibility of insomnia as an effect modifier we will stratify randomization based on presence of insomnia (Insomnia Severity Index ≥ 10).¹⁵ We will follow the CONSORT 2010 checklist for randomization. Sequence generation: [name] will generate the randomization sequence using the R statistical software. Allocation concealment: the randomization sequence will remain concealed to research staff. Research staff who are enrolling participants will not know the allocation sequence in advance. Implementation: after a participant is determined eligible, research staff will contact [name] about treatment

allocation. *Consideration of sex as a biological variable*: groups will be stratified by sex because women are more likely to experience the death of their spouse compared to men (75% of participants in our pilot RCT were women).

Efficacy Analyses

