We will employ repeated-measures mixed-effects ANCOVA, which extend the standard repeated measures ANCOVA to allow for missing values, error structures other than compound symmetry, and measurements taken non-equal intervals. The test of efficacy for the intervention will be analyzed under an 'intent-to-treat' criteria.¹⁶ We will control for important baseline variables, including baseline levels of the outcome of interest (HAM-D), and, to extend the 'intent to treat' mechanism, all participants randomized into the study are included in all analyses irrespective of protocol violations arising post randomization. Inclusion of covariates may add precision to the estimates and allow us to assess the generalizability of the effects across the covariates. The list of covariates, (e.g., age, sex, race, medical co-morbidity) will be developed prior to any analysis. Statistical significance will be $\alpha=0.05$ (two-tailed). Controlling for baseline variables will allow us to assess both group differences (main effect of group) and for differential change over time for depression symptoms repeatedly over the course of the study (group X time interaction). If the group X time interaction is significant, we will assess in post hoc tests, where the two groups differ. If no group X time interaction, will test main effects only. In all analyses, the time (in days) since spousal death will be included as a covariate.

Missing Data

Missing values are inevitable in clinical research. Participants may drop out from the intervention for a variety of reasons, including time constraints, competing interests, and personal choice. If, despite our projections, there is substantial missing values, we will incorporate the impact of censoring due to lost to follow-up and dropout into the analysis to assess if possible bias exists. We will use pattern mixture models to evaluate if the missing mechanism has an influence on parameter estimates. We will use standard multiple imputation for conducting inference on full data effects. If our data are not missing at random (MAR)¹⁷ (i.e., pattern of ‘missingness’ is similar between groups), we will assess the impact of missingness on our estimates and will use pattern mixture models to check that there are no untoward influences of missing values. Pattern mixture models compare the outcomes (trajectories) across the various patterns of missing data.¹⁸

Sample Size and Power Calculations

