Power calculations for each aim were calculated assuming effect sizes as estimated from the preliminary data collected in 55 subjects in the PI’s pilot RCT. Calculations were conducted in R using the pwr and powerMediation packages. All tests were conducted at level $\alpha=0.05$. In the preliminary data, a Cohen’s d of 0.616 was observed for the change in depression scores after treatment between WELL and EUC. Under this effect size, there is an estimated 96.3% power to detect differences in changes in depression among treatment groups in Aim 1.

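### The two-step efficacy rule (interaction, then post hoc tests, otherwise main effect) does not hold the stated two-sided 0.05, and the available text fixes no primary contrast or time point

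*Combined protocol and SAP*

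**What the plan says.** All references are to the combined protocol and SAP.

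- **Section 3, Efficacy Analyses.** A repeated-measures mixed-effects ANCOVA is tested at two-tailed 0.05. On baseline: "We will control for important baseline variables, including baseline levels of the outcome of interest (HAM-D". The test rule is two sentences: "If the group X time interaction is significant, we will assess in post hoc tests, where the two groups differ" and "If no group X time interaction, will test main effects only". The number of post hoc tests, the visits, any adjustment and any division of alpha are not given.
- **Section 3, Descriptive Statistics.** One stated purpose is "comparing the change between the intervention and enhanced usual care group with regards to the primary outcome (depression symptoms". This names an outcome and a type of comparison, but no visit.
- **Section 3, Sample Size and Power Calculations.** Power for Aim 1 is 96.3%, from a Cohen's d of 0.616 "observed for the change in depression scores after treatment between WELL and EUC", with every test at 0.05.
- **Section 1, Overview.** The intervention lasts 12 weeks, and "Subjects will be followed for 12 months after the intervention".
- **Section 2, Table 1.** The delivery row lists "Monitoring checklists for each session (BL, T2, T3, T4, T5", which suggests up to four post-baseline occasions.

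Figure 1 (study design) is not reproduced in the text available, and Aim 1 is mentioned but not stated there. Either may name a time point.

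**The concern.** The rule offers two routes to a positive result, each with its own 0.05. If the interaction is significant, the groups may be declared different at whichever visit the post hoc tests pick out. If it is not, the main effect has a fresh 0.05. Nothing in the text caps the total.

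The choice of route also changes the question answered. One route reports a difference at some visit, the other an average over follow-up, and the observed interaction decides between them. A reader could not say beforehand which effect the trial was designed to estimate.

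The gate may not ask about efficacy at all. If baseline HAM-D is only a covariate and the follow-up visits are the outcomes, group by time asks whether the benefit differs between visits. A benefit that appears after treatment and persists unchanged produces no interaction, and that is not the question the trial was powered for.

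**Working it through.** **Inputs from the document.** N = 150 with 1:1 allocation, so 75 per arm; two-sided alpha 0.05; d = 0.616; stated power 96.3%; pilot retention 93%.

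**Assumptions.** Two, three or four follow-up visits (four if each of T2-T5 includes the HAM-D); complete data; within-person correlation of baseline-adjusted scores of compound symmetry 0.5, compound symmetry 0.7, or first-order autoregressive 0.6. The document gives none of these.

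**1. The plan's own figure.** For a two-sample comparison with n per arm, the noncentrality is d × √(n/2) = 0.616 × √37.5 = 3.77. The normal approximation gives Φ(3.77 − 1.96) = 96.5%, and the noncentral t with 148 degrees of freedom gives 96.3%. The stated power is reproduced, and it is the power of one after-treatment comparison. With 0.93 × 75 = 69.75 analysed per arm it would be about 95.1%.

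**2. Ceiling for the rule.** If a significant interaction or a significant main effect each counts as efficacy and the two tests are independent, the error is 0.05 + 0.95 × 0.05 = 0.0975. It cannot exceed 0.10 under any dependence.

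**3. Simulation of the rule with no effect at any visit.** The interaction was tested by Hotelling's T² across follow-up visits, the main effect by a t-test on the visit average, and the post hoc comparisons by a t-test at each visit. There were 400,000 replicates per scenario (Monte Carlo standard error about 0.04 percentage points). Ranges are over the three correlations.

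| What counts as a positive trial | 2 visits | 3 visits | 4 visits |
|---|---|---|---|
| Interaction plus an unadjusted visit test, otherwise main effect | 6.03-6.55% | 6.36-7.08% | 6.52-7.57% |
| Same, Bonferroni over visits | 5.51-5.83% | 5.50-5.83% | 5.41-5.91% |
| Same, Scheffé | 5.24-5.46% | 5.06-5.18% | 4.91-5.03% |
| Same, Bonferroni over all group-by-time cell pairs | 4.90-4.96% | 4.90-4.92% | 4.85-4.93% |

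Over all visit counts:

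- Either significant test counts as efficacy: 9.69-9.77%.
- Interaction alone is the efficacy test: 4.93-5.03%.
- One pre-specified visit contrast: 4.96-5.03%.
- False claims in favour of WELL only: 2.99-3.81% unadjusted and 2.72-2.96% with Bonferroni over visits, against a nominal 2.5%.

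A wider set of correlations (compound symmetry 0.3 to autoregressive 0.8) moves the unadjusted figure to about 5.8-8.3%.

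**4. A sustained effect of 0.616 SD at every follow-up visit** (100,000 replicates). With follow-up visits only as outcomes, the interaction is significant in 4.92-5.20% of trials, which is its null rate. The full rule still detects the effect in 98.3-99.8%, because the main-effect route catches it. The visit average tested by itself has 98.2-99.8% power.

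**The case against.** The strongest reply is that the text does point to a contrast. Its stated purpose is to compare change in depression symptoms, and the power statement ties Aim 1 to change after treatment. That is fair as far as it goes, and the remedy below adopts that contrast. But a power sentence does not designate the primary test, and the Efficacy Analyses prescribe a different procedure without referring to it. If Figure 1 or the aims name a time point, the two-step rule would still conflict with a single test at that time.

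Second, the excess depends on what counts as success, which the plan does not define. Treating the interaction as the sole efficacy test, or using Scheffé or all-pairs post hoc tests, keeps the error close to 5%. This stands, and is why the claim is that the rule does not guarantee 0.05, not that it breaches it on every reading. The plan specifies none of these safeguards.

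Third, the weak interaction test for a sustained effect arises only if baseline is left out of the outcomes. With baseline kept as an outcome, the interaction has power of about 89-98% for a sustained effect, with 0.616 taken on the change to the first visit. The document does not settle which model applies, so that figure is conditional and is not the power of the plan's rule.

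Fourth, the visit count is inferred from a fidelity checklist and the correlations are assumed. This also stands: the size of the excess is a range under stated assumptions.

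**Conclusion.** The concern holds. Followed on its natural reading, the rule exceeds its own 0.05: 6.0-7.6% with unadjusted visit tests and 5.4-5.9% with Bonferroni over visits, given 75 per arm, complete data, two to four follow-up visits and the correlations above. The 9.7-9.8% figure applies only if a significant interaction or main effect is itself taken as efficacy.

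The inflation is modest and power for a sustained effect does not suffer. The defect that needs no simulation is that the available text leaves the data to choose the primary estimand, while the stated power belongs to one contrast that the test rule never adopts. This should be fixed. The gap in the wording is certain; the exact size of the excess is not.

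**What to change.** Before any unblinded analysis, replace the two sentences of the test rule with one pre-specified contrast from the mixed model, tested once at two-sided 0.05 whatever the interaction shows.

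- **Preferred contrast:** the baseline-adjusted difference in HAM-D, WELL minus enhanced usual care, at the after-treatment assessment. It is the closest match to the power statement: 5.0% error, and 96.3% power if 0.616 applies on the baseline-adjusted scale and all 150 are analysed.
- **Alternative:** the average over follow-up, which suits the stated wish to "modify the trajectories of depressive symptoms in bereaved elders". It controls error equally well, but power must be restated; 98.2-99.8% applies only if 0.616 SD holds at every visit.
- **Everything else:** make the interaction and the remaining visits or contrasts secondary, under Holm or a fixed sequence. State whether baseline is a covariate or one of the repeated outcomes.
- **If Figure 1 or the aims already name a primary time point,** repeat it in the Efficacy Analyses.

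The cost is a dated SAP wording change, with no effect on sample size or data collection. With the after-treatment contrast as primary, durability over the 12-month follow-up becomes a secondary claim. The fidelity section describes some conduct in the past tense; if outcomes have already been compared by arm, the contrast must be reported as chosen post hoc.
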